APPENDIX 2: TUBERCULOSIS SCREENING

All subjects will have undergone screening for a history of TB infection and testing for latent/active TB infection in the APD334-302 study. Their medical history review must include specific questions about a history of TB or known occupational or other personal exposure to individuals with active TB. Subjects should be asked about past testing for TB, including chest radiograph results and results of interferon-gamma release assay (IGRA, eg, QuantiFERON-TB Gold In-Tube, T-SPOT TB) or response to tuberculin skin test (TST) and history of Bacillus Calmette-Guérin vaccination.

- a. The IGRA or TST is NOT required at Week 52 for subjects with a history of active/latent TB infection.
 - Subjects receiving TB prophylaxis treatment during the APD334-302 must have documentation of treatment with an acceptable TB prophylaxis treatment regimen (with a plan to complete the TB treatment course during study participation) to qualify for enrollment. It is the responsibility of the investigator to verify the adequacy of previous TB treatment and provide appropriate documentation (Direct Observation Therapy report where available).
- b. Acceptable TB prophylaxis treatment regimens for latent TB is defined according to local country guidelines. If no local country guidelines for the treatment of latent TB exist, WHO guidelines must be followed.

c. Resources

 For the WHO guidelines for the treatment of latent TB visit: https://apps.who.int/iris/bitstream/handle/10665/44165/9789241547833_eng.pdf;jsessionid=115F807C3008D688F75118AF16EA53F0?sequence=1

Etrasimod Program
Tuberculosis Screening Questionnaire
Created by Arena Pharmaceuticals, Inc
Version 1.0, 17Jan2020
Site #:
Subject #:

Tuberculosis Screening Questionnaire Source Document Worksheet

Instructions:

- This source document worksheet should be completed by the PI or delegated site staff.
- 2. This source document worksheet should NOT be given to the subject for completion.
- 3. Please complete for ALL subjects during the Screening visit.
- 4. Please complete at every study visits for subjects who are receiving TB prophylaxis treatment (until the TB prophylaxis treatment course is completed) and at designated post-baseline study visits (per protocol schedule of assessments) for subjects who reside in countries with a high burden of TB or multi-drug resistant (MDR) TB as identified by WHO. The current WHO TB high burden country (HBC) and MDR TB HBC lists can be found at the following URL: http://www.stoptb.org/countries/tbdata.asp.
- 5. Enter all applicable information on the corresponding eCRF.

Was the Tuberculosis Screening questionnaire completed? Yes/No

If yes, please enter completion date (DD/MM/YYYY): _____

If no, specify reason:

Date of completion of TB Screening Questionnaire, if applicable: _____

Study Visit Number: ____

Section 1: Questions to ask the subject

^{*}Time frame: in the past year or since your last study visit.

Have you experienced any of the following symptoms?*	
a) A productive cough (coughing up phlegm) for more than 3 weeks	Yes/ No
b) Hemoptysis (coughing up blood)	Yes/ No
c) Unexplained weight loss	Yes / No
d) Fever, chills, or night sweats for no known reason	Yes / No
e) Persistent shortness of breath (difficulty breathing)	Yes/No
f) Unexplained fatigue	Yes/No
g) Chest pain	Yes / No

Etrasimod Program	
Tuberculosis Screening Questionna	ire
Created by Arena Pharmaceuticals,	Inc
Version 1.0, 17Jan2020	

Site #:	
Subject #:	

Have you had contact with anyone with active tuberculosis disease?*	Yes/No
3. Have you been diagnosed with latent TB infection?	Yes / No
a) If yes, list medication(s) used to treat latent TB infection and treatment dates (please ensure listed on Concomitant Medication Source Log and eCRF, as applicable). Medication #1:	
Start date of Medication #1:	
Expected stop date of Medication #1:	
Have you missed taking any doses of Medication #1?	Yes / No
Dates of Missed Doses:	100.110
# of Missed Doses:	
Medication #2:	
Start date of Medication #2:	
Expected stop date of Medication #2:	
Have you missed taking any doses of Medication #2?	
Dates of Missed Doses:	Yes / No
# of Missed Doses:	
Medication #3:	
Start date of Medication #3:	
Expected stop date of Medication #3:	
Have you missed taking any doses of Medication #3? Dates of Missed Doses:	Yes/No
# of Missed Doses:	
Medication #4:	
Start date of Medication #4:	
Expected stop date of Medication #:	
Have you missed taking any doses of Medication #4?	Yes/No
Dates of Missed Doses:	
# of Missed Doses:	

Please provide details to any question answered "Yes."

Tube	simod Program erculosis Screening Questionnaire
	ted by Arena Pharmaceuticals, Inc. .ion 1.0, 17Jan2020
	#:
Subj	ject #:
Sec	ction 2: To be completed by the investigator
I.	The participant is on concomitant medication(s) with immunosuppressive effects: Yes/No
	If yes, specify medication(s) (name, dosage):
	Medication #1:
	Medication #2:
	Medication #3:
	Medication #4:
II.	TB QuantiFERON or Tuberculin Skin Test result: Date:
	Chest x-ray/computer tomography (CT) scan done to rule out pulmonary TB? Yes/No
	If yes, date of chest x-ray or CT scan:
	Any evidence of active pulmonary TB disease on chest x-ray or CT scan? Yes / No
	Other assessment completed? Yes/No
	If yes, specify assessment:
	If yes, date of other assessment:
	Any evidence of active TB disease on assessment? Yes / No
III.	Upon review of the responses and discussion with the participant, I recommend the following:
	Perform screening test for latent TB infection
	Perform additional assessments to rule out active TB disease
	Refer to physician TB expert for evaluation and treatment
	Follow up at the next TB-designated study visit and repeat TB screening questionnaire

APPENDIX 3: MAYO CLINIC SCORE – SAMPLE

Mayo Scoring System for Assessment of Ulcerative Colitis Activity

Stool frequency^a

0 = Normal number of stools for this subject

1 = 1 to 2 stools more than normal

2 = 3 to 4 stools more than normal

3 = 5 or more stools more than normal

Subscore: 0 to 3

Rectal bleedingb

0 = No blood seen

1 = Streaks of blood with stool less than half the time

2 = Obvious blood with stool most of the time

3 = Blood alone passes

Subscore: 0 to 3

Findings on endoscopy^c

0 = Normal or inactive disease

1 = Mild disease (erythema, decreased vascular pattern)

2 = Moderate disease (marked erythema, lack of vascular pattern, friability, erosions)

3 = Severe disease (spontaneous bleeding, ulceration)

Subscore: 0 to 3

Physician's Global Assessment^d

0 = Normal

1 = Mild disease

2 = Moderate disease

3 =Severe disease

Subscore: 0 to 3

The Mayo score ranges from 0 to 12, with higher scores indicating more severe disease.

- a Each subject serves as his or her own control to establish the degree of abnormality of the stool frequency.
- b The daily bleeding score represents the most severe bleeding of the day.
- c The endoscopy subscore will be determined by qualified personnel at a central laboratory.
- d The Physician's Global Assessment acknowledges the 3 other criteria, the subject's daily recollection of abdominal discomfort and general sense of well-being, and other observations, such as physical findings and the subject's performance status.

APPENDIX 4: HISTOLOGICAL SCORING INDICES

Geboes Grading System

The Geboes Grading System is a stepwise grading system used for the evaluation of microscopic inflammation and histopathologic disease activity in UC. The microscopic appearance of the mucosa is categorized into 6 grades. A decrease of the Geboes Score grading system to Grade zero (0) or one (1) indicates mucosal healing (Geboes 2000).

Nancy Histological Index

The Nancy Histological Index is a validated index for assessing histological disease activity in UC. It is composed of three histological items defining five grades of disease activity: absence of significant histological disease (Grade 0), chronic inflammatory infiltrate with no acute inflammatory infiltrate (Grade 1), mildly active disease (Grade 2), moderately active disease (Grade 3), and severely active disease (Grade 4). The presence of ulceration on the biopsy specimen corresponds to severely active disease (Grade 4). If there is no ulceration, acute inflammatory cells infiltrate (presence of neutrophils) is assessed. Moderate or severe acute inflammatory cells infiltrate corresponds to moderately active disease (Grade 3), while mild acute inflammatory cells infiltrate correspond to mildly active disease (Grade 2). If there is no acute inflammatory cells infiltrate, assessment of chronic inflammatory infiltrate (lymphocytes and plasmacytes) is made. A biopsy specimen showing moderate or marked chronic inflammatory infiltrate (Grade 1). A biopsy specimen showing mild or no chronic inflammatory infiltrate corresponds to absence of significant histological disease (Grade 0) (Marchal-Bressenot 2017).

Robarts Histopathology Index

[figure not shown]
The RHI is an evaluative index, derived from the Geboes score, that is designed to be reproducible and responsive to clinically meaningful change in disease activity over time. The total RHI score ranges from 0 (no disease activity) to 33 (severe disease activity) and is calculated as follows: RHI = $1 \times \text{Chronic}$ inflammatory infiltrate + $2 \times \text{Lamina}$ propria neutrophils + $3 \times \text{Neutrophilis}$ in epithelium + $5 \times \text{Erosion}$ or ulceration (Mosli 2017).

APPENDIX 5: GUIDANCE FOR THE ASSESSMENT OF POTENTIAL PROGRESSIVE MULTIFOCAL LEUKOENCEPHALOPATHY

If a subject exhibits signs and symptoms suspicious for PML, the Investigator must interrupt study treatment and perform a targeted neurologic examination to assess for signs of PML, which are diverse, progress over days to weeks, and may include progressive weakness on one side of the body or clumsiness of limbs or difficulty with walking or writing or fine motor skills, disturbance of vision, changes in thinking, memory and orientation leading to confusion and (expressive aphasia), and/or agnosia (receptive aphasia). Consultation with a local neurologist may be warranted, as presented in the PML case evaluation algorithm in Figure 3.

The Medical Monitor should be informed of any suspected cases of PML and, if needed, will facilitate investigator/local neurologist consultation with PML medical experts on the independent adjudication committee.

Figure 3: Progressive Multifocal Leukoencephalopathy Case Evaluation Algorithm

CE, contrast-enhanced; CSF, cerebral spinal fluid; IAC, independent adjudication committee; IP, investigational product; JCV, John Cunningham Virus; MRI, magnetic resonance imaging; PCR, polymerase chain reaction; PML, progressive multifocal leukoencephalopathy; r/o, rule out.

Note: IP dosing may resume, and no further evaluation is needed if the Investigator assessment reveals no objective signs of PML, the local neurologist confirms that the subject does not have PML, or the IAC's review of the evidence concludes that PML is ruled out.

C _{trough,ss}	Average steady-state trough plasma concentration
CV	coefficient of variation
DBP	Diastolic blood pressure
DLCO	diffusing capacity of the lungs for carbon monoxide
EAIR	exposure-adjusted incidence rate

Abbreviation	Explanation
ECG	electrocardiogram
eCRF	electronic case report form
eDISH	evaluation of Drug-Induced Serious Hepatotoxicity
CCI	[REDACTED]
ES	endoscopic score
FAS	Full Analysis Set
FCP	fecal calprotectin
FCS	fully conditional specification
FDA	Food and Drug Administration
FEF	Forced Expiratory Flow
FEV1	Forced Expiratory Volume in 1 second
FVC	Forced Vital Capacity
GGT	gamma-glutamyl transferase
HR	heart rate
HRQoL	Health-Related Quality of Life
hs-CRP	high-sensitivity C-reactive protein
IBDQ	Inflammatory Bowel Disease Questionnaire
ICF	informed consent form
JAK	Janus kinase
LLQ	limit of quantification
LOESS	locally estimated scatterplot smoothing
LS	Least squares
MAR	missing at random
MCMC	Markov Chain Monte Carlo
MCS	mental component summary
MedDRA	Medical Dictionary for Regulatory Activities
mFAS	modified Full Analysis Set
MMRM	mixed-effect model with repeated measures
MMS	modified Mayo score
MNAR	missing not at random
NCS	Not Clinically Significant

Abbreviation	Explanation
NHI	Nancy Histologic Index
NRI	Nonresponder imputation
NRS	Numeric Rating Scale
OCT	optical coherence tomography
OLE	open-label extension
PCS	physical component summary
PFT	pulmonary function test
PGA	Physicians Global Assessment
PK	pharmacokinetics
PRES	posterior reversible encephalopathy syndrome
PT	preferred term
RB	rectal bleeding
CCI	[REDACTED]
RNA	ribonucleic acid
SAE	serious adverse events
SAP	Statistical Analysis Plan
SBP	Systolic blood pressure
SD	standard deviation
SDTM	Study Data Tabulation Model
SF	stool frequency
SF-36	36-Item Short Form Health Survey
SI	International System of Units
SOC	system organ class
SS	Steady state
TB	Tuberculosis
TEAE	treatment-emergent adverse event
TLC	Total Lung Capacity
TME	targeted medical event
TMS	total Mayo score
TNF α	tumor necrosis factor alpha
UC	ulcerative colitis

Abbreviation	Explanation
UC-PRO/SS	ulcerative colitis patient-reported outcomes signs and symptoms
ULN	Upper limit of normal
ULQ	upper limit of quantification
WHO	World Health Organization
WPAI-UC	Work Productivity and Activity Impairment Questionnaire – Ulcerative Colitis

1. INTRODUCTION

This statistical analysis plan (SAP) describes the statistical rationale, methods, rules and conventions to be used in the presentation and analysis of efficacy, safety, pharmacokinetic, health-related subject-reported outcome and biomarker data for Protocol APD334-308. It describes the data to be summarized and analyzed, including specifics of the statistical analyses to be performed (ICH 1998). This SAP is based on protocol version Original 0.0, dated 15 April 2020.

2. STUDY Objectives

2.1. Primary Objective

The primary objective is to assess the efficacy of etrasimod on clinical remission in Japanese subjects with moderately to severely active ulcerative colitis (UC) at timepoints up to 52 weeks of treatment (12 weeks in Study APD334-302 plus 40 weeks in Study APD334-308).

2.2. Secondary Objectives

The secondary objective is to assess the efficacy of etrasimod on clinical response, symptomatic response and remission, endoscopic changes, corticosteroid-free remission, and mucosal healing in Japanese subjects with moderately to severely active UC at timepoints up to 52 weeks of treatment (12 weeks in Study APD334-302 plus 40 weeks in Study APD334-308).

2.3. Safety Objective

The safety objective is to assess the long-term safety of etrasimod in Japanese subjects with moderately to severely active UC after daily doses of 2 mg for up to 52 weeks (12 weeks in Study APD334-302 plus 40 weeks in Study APD334-308).

2.4. Other Objectives

Other objectives include evaluation of etrasimod pharmacokinetics (PK) and the effect of etrasimod on health-related subject-reported outcomes and biomarkers.

2.5. Estimands

The primary and key secondary efficacy estimands to support regulatory decisions are described in Table 1. The analyses will be performed on the Full Analysis Set (FAS) as defined in Section 5.3. Other secondary efficacy variables (specified in Section 16.3.1) will have the population, intercurrent event handling strategy and population-level summary measure similar to the primary estimand. Supplementary analyses for the primary and the key secondary estimands will be performed on the modified Full Analysis Set (mFAS) and the Per Protocol populations, respectively .

Table 1 List of Primary and Key Secondary Estimands

Estimand	Definition	Attribute			
		Population	Variable/Endpoint	Intercurrent Event Handling Strategy	Population-Level Summary Measure
Primary Estimand 1	Efficacy of etrasimod on clinical remission at Week 52	Enrolled subjects who receive at least 1 dose of etrasimod	The proportion of subjects with SF = 0 (or = 1 with a \geq 1-point decrease from Baseline in APD334-302), RB = 0, and ES \leq 1 (excluding friability) at Week 52	Subjects with missing data for any reason (including discontinuation due to lack of efficacy or adverse event related to UC) or any of the 3 intercurrent events ^a before the efficacy assessment will be treated as nonresponders.	Difference between etrasimod and placebo in proportion of responders at Week 52
Key Secondary Estimand 1	Efficacy of etrasimod on endoscopic improvement at Week 52	Enrolled subjects who receive at least 1 dose of etrasimod	The proportion of subjects with ES of \leq 1 (excluding friability) at Week 52	Same as the intercurrent event handling strategy for the primary estimand	Difference between etrasimod and placebo in proportion of responders at Week 52
Key Secondary Estimand 2	Efficacy of etrasimod on symptomatic remission at Week 52	Enrolled subjects who receive at least 1 dose of etrasimod	The proportion of subjects with SF = 0 (or = 1 with a \geq 1-point decrease from Baseline in APD334-302) and RB = 0 at Week 52.	Same as the intercurrent event handling strategy for the primary estimand	Difference between etrasimod and placebo in proportion of responders at Week 52
Key Secondary Estimand 3	Efficacy of etrasimod on corticosteroid-free clinical remission at Week 52	Enrolled subjects who receive at least 1 dose of etrasimod	The proportion of subjects with clinical remission at Week 52, while not receiving corticosteroids for 12 or more weeks in the 40-Week Treatment Period	Same as the intercurrent event handling strategy for the primary estimand	Difference between etrasimod and placebo in proportion of responders at Week 52
Key Secondary Estimand 4	Efficacy of etrasimod on mucosal healing at Week 52	Enrolled subjects who receive at least 1 dose of etrasimod	The proportion of subjects with ES of \leq 1 (excluding friability) with histologic remission measured by a Geboes Index score $<$ 2.0 at Week 52	Same as the intercurrent event handling strategy for the primary estimand	Difference between etrasimod and placebo in proportion of responders at Week 52

Estimand	Definition	Attribute			
		Population	Variable/Endpoint	Intercurrent Event Handling Strategy	Population-Level Summary Measure
Key Secondary Estimand 5	Efficacy of etrasimod on sustained clinical remission	Enrolled subjects who receive at least 1 dose of etrasimod	The proportion of subjects with sustained clinical remission (clinical remission at both Weeks 12 and 52)	Same as the intercurrent event handling strategy for the primary estimand	Difference between etrasimod and placebo in proportion of responders

^a Intercurrent events include: 1) initiate a rescue medication for UC, 2) have an increase in dose over Baseline levels in their existing UC medication, or 3) have colectomy or ileostomy before the efficacy assessment.

This SAP will analyze on the data collected in APD334-308 (from Week 16 to Week 52). The scope of analysis will be specified in Table/Listing/Figure shells. To fully address study primary objective “to assess the efficacy of etrasimod on clinical remission in Japanese subjects with moderately to severely active ulcerative colitis (UC) at timepoints up to 52 weeks of treatment (12 weeks in Study APD334-302 plus 40 weeks in Study APD334-308)”, after database lock and treatment unblinding, an integrated analysis of Study APD334-302 and Study APD334-308 will be performed for all Japanese subjects who had enrolled in ADP334-302 and covers the complete data from APD334-302 and to APD334-308.

3. STUDY Design

3.1. General Description

[figure not shown]
This is a multicenter, double-blind, placebo-controlled extension study of APD334-302 (12-week, randomized, double-blind, placebo-controlled induction study) to evaluate the efficacy and safety of etrasimod 2 mg in Japanese subjects with moderately to severely active UC. The study consists of a 40-Week Treatment Period and a 4-Week Follow-Up Period (Figure 1).

Japanese subjects who completed the Week 12 visit of Study APD334-302 are eligible for Study APD334-308. The Week 12 visit of Study APD334-302 serves as the Day 1 visit of this study. Subjects will continue with the same blinded treatment assigned in Study APD334-302 for a total treatment duration of 52 weeks (12 weeks in Study APD334-302 plus 40 weeks in Study APD334-308).

Disease worsening will be monitored by Investigators through the treatment period of Study APD334-308. Subjects who either experience disease worsening or complete all study procedures at Week 52 will have the option to enroll into the APD334-303 OLE study if they meet all eligibility criteria.

Subjects who discontinue from the study and do not participate in the OLE study will have 2-Week and 4-Week Follow-Up visits after the last on-treatment visit/Early Termination visit.

Figure 1 Study Design

3.2. Schedule of Events

Schedule of events can be found in Appendix Table 7 of the protocol.

3.3. Changes to Analysis from Protocol

Note that Ulcerative Colitis Patient-Reported Outcomes Signs and Symptoms (UC-PRO/SS) was never implemented in Study APD334-308. Therefore, no summary is planned.

Protocol Section 10.12.1 Efficacy Analysis specified “The primary analysis of the proportion-based efficacy endpoints will be carried out using the Cochran-Mantel-Haenszel (CMH) method, stratified by (a) naive to biologic or JAK inhibitor therapy at APD334-302 study entry (yes or no), (b) baseline corticosteroid use (yes or no), and (c) baseline disease activity (MMS: 4 to 6 or 7 to 9).” Due to the limited number of subjects enrolled in APD334-308 and globally stratified randomization do not control for treatment balance in Japanese subjects, above mentioned CMH method was removed from for APD334-308 efficacy analyses.

4. PLANNED ANALYSES

The following analyses will be performed for this study:

- Final Analysis for APD334-308 data only
- An integrated analysis that covers the complete data from APD334-302 and to APD334-308. This analysis will be specified in a separate analysis plan

4.1. Interim Analysis

There is no planned interim analysis for this study.

4.2. Final Analysis

All final, planned analyses identified in this SAP will be performed by IQVIA Biostatistics following Sponsor (Arena Pharmaceuticals, Inc., hereafter referred to as Arena) authorization of the SAP, database lock, analysis sets, and unblinding of treatment. After Arena has authorized breaking of the study blind, the final analysis will be performed.

Any, post-hoc, **CCI** analyses completed to support planned study analyses, which were not identified in this SAP, will be documented and reported in the clinical study report (CSR). Any results from these unplanned analyses will also be clearly identified in the text of the CSR (ICH, 1995).

5. ANALYSIS SETS

Agreement and authorization of subjects included/excluded from each analysis set will be conducted prior to the unblinding of the study.

5.1. SCREENED SET

The Screened Set will consist of all subjects who sign informed consent to participate in the study. No analysis is planned in this set.

5.2. RANDOMIZED SET

The Randomized Set will consist of all Japanese subjects who are randomized to study treatment at the start of Study APD334-302. No analysis is planned in this set.

5.3. FULL ANALYSIS SET [FAS]

The FAS will consist of all enrolled subjects who signed informed consent form and receive at least 1 dose of study treatment during Study APD334-308. Subjects will be summarized by the treatment group to which they were randomized in Study APD334-302, regardless of the treatment actually received during Study APD334-308.

5.4. PER PROTOCOL SET

Due to a small number of subjects in APD334-308 who meet the Per Protocol criteria, efficacy analyses in Per Protocol Set will not be performed.

5.5. MODIFIED FULL ANALYSIS SET

The mFAS will consist of all enrolled subjects who receive at least 1 dose of study treatment and have a Baseline and at least 1 post enrollment measurement in APD334-308. Subjects will be summarized by treatment to which they were randomized, regardless of treatment actually received. Note that the mFAS can vary between endpoints since some subjects may have the data needed for inclusion in the mFAS for some endpoints, but not other endpoints. Also note, since the Mayo component scores on the disease worsening CRF are manually entered by sites from another CRF, these scores will not be used in the derivation of mFAS for measurement of either MMS or any of its component scores.

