^a Subjects are continuing treatment from 12-week Study APD334-302. The Week 12 visit of Study APD334-302 serves as the Day 1 visit of this study. Subjects will be reconsented for this study. Screening for eligibility will be performed for Study APD334-302 and only modified eligibility criteria will be assessed for this study (Section 4.1 and Section 4.2). Visit labels and windows are relative to Week 0/Day 1 of Study APD334-302.

b Subjects discontinuing treatment prior to Week 52/Day 365 should have an Early Termination visit within 7 days of the last study treatment administration and before initiation of any new treatments. If a subject discontinues at or before Week 16, a sigmoidoscopy and biopsy are not required. For subjects with worsening disease or who complete Week 52 and wish to enter the APD334-303 OLE study, the Week 52/Early Termination visit will be used to assess eligibility for the OLE study.

^c For subjects discontinuing study treatment, 2-Week and 4-Week Follow-Up visits should be scheduled 2 weeks and 4 weeks after the Week 52/Early Termination visit and the indicated assessments performed; however, if the Early Termination or Week 52 visit is ≥ 2 weeks after the last dose of study treatment, the 2-Week Follow-Up visit is not required; however, the 4-Week Follow-Up visit should be scheduled and completed. If the Early Termination or Week 52 visit is ≥ 4 weeks after the last dose of study treatment, the 4-Week Follow-Up visit is not required. If the absolute peripheral lymphocyte count is not within normal limits at the 4-Week Follow-Up visit, subjects should return for CBC with differential according to local standard of care (captured as subsequent Follow-Up visit or unscheduled visit).

d Subjects will continue eDiary entries through the Eligibility Visit and during the treatment period. The subject eDiary will be reviewed by study site staff at each treatment visit.

^e The Week 52 MMS will be calculated using the Week 52 proctosigmoidoscopy and SF and RB scores completed by the subject 7 days prior to the visit using the 3 most recent consecutive days prior to the actual day of the study visit excluding the day of bowel preparation.

- f Stool frequency and RB subject-reported outcomes recorded daily using eDiary. The RB and SF subscores will be calculated as indicated in Section 9.7.1.

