16.1.2. Missing Data Methods for Primary Efficacy Variable

Subjects who 1) discontinue the study for lack of efficacy, or adverse event related to UC, 2) initiate a rescue medication for UC, 3) have an increase in dose over Baseline levels in their existing UC medication, or 4) have rescue medical procedure (e.g., colectomy, ileostomy, or sigmoidectomy) during the study as confirmed after blinded review by clinical and medical team members before study unblinding will be considered to have a known (i.e., non-missing) outcome of nonresponse in the analysis of all efficacy endpoints at any subsequent timepoints, including the primary endpoint. The rescue medications will be identified by the Arena clinical team during blinded data review. Refer to APPENDIX 6APPENDIX 6 for the definition of rescue therapies (medication and medical procedures). In scenarios #2 and #3 above, if a subject has efficacy measurement collected after the initiation or dose increase from Baseline of UC medication, the observed data will be censored at the time of initiation or dose increase and they will be considered having a nonresponse. Subjects in all 4 scenarios above may still be included in the respective Per Protocol Set, provided they do not violate other criteria for Per Protocol Set. For example, they will be excluded from the respective Per Protocol Set if they initiate a prohibited medication before Week 52 efficacy assessment that can affect efficacy of the study

treatment and the indication is unrelated to UC.

Analysis visits will be mapped as per Section 6.4 before any missing data imputation method is applied.

Subjects with missing efficacy outcome will be included in the primary analyses using single imputation as nonresponder. Supplementary analyses of efficacy outcomes will be performed in modified Full Analysis Set with data as observed.

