16.1.4. Supplementary Analysis of Primary Efficacy Variables

The primary analysis as described in Section 16.1.3 will be repeated using the mFAS (with data as observed) as supplementary analyses.

Key Secondary Efficacy

Key secondary efficacy endpoints are defined in Section 16.2. In general, all the primary and supplementary analyses planned for the primary endpoints in Section 16.1.3 and Section 16.1.4 will be repeated for each key secondary efficacy endpoint (Table 3). No Multiplicity adjustments will be conducted as discussed in Section 8.4.

Table 3 Planned Analyses by Endpoint

Endpoint	Primary Analysis in FAS	Supplementary Analyses in mFAS
Primary endpoint: Clinical remission at Week 52	X	X
Key secondary endpoints:		
Endoscopic improvement at Week 52	X	X
Symptomatic remission at Week 52	X	X
Corticosteroid-free clinical remission at Week 52	X	X
Mucosal healing at Week 52	X	X
Sustained clinical remission at Week 12 and at Week 52	X	X

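### The mFAS entry rule can drop known nonresponders who have no APD334-308 endoscopy from the supplementary analyses of endoscopy-based endpoints

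*SAP*

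**What the plan says.** SAP 5.5 admits to the mFAS enrolled subjects who "receive at least 1 dose of study treatment and have a Baseline and at least 1 post enrollment measurement in APD334-308". Membership is specific to the endpoint: the "mFAS can vary between endpoints since some subjects may have the data needed for inclusion in the mFAS for some endpoints" but not for others. Mayo scores from the disease-worsening form do not help a subject in, because "these scores will not be used in the derivation of mFAS for measurement of either MMS or any of its component scores".

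SAP 16.1.2 lists four failure scenarios: stopping the study for lack of efficacy or a UC-related adverse event, starting rescue medication, raising the dose of existing UC medication above Baseline, and a rescue procedure. Once confirmed in blinded review, these subjects "will be considered to have a known (i.e., non-missing) outcome of nonresponse in the analysis of all efficacy endpoints at any subsequent timepoints". For the primary analyses, "Subjects with missing efficacy outcome will be included in the primary analyses using single imputation as nonresponder". The section then adds: "Supplementary analyses of efficacy outcomes will be performed in modified Full Analysis Set with data as observed".

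SAP 16.1.4 carries this through: "The primary analysis as described in Section 16.1.3 will be repeated using the mFAS (with data as observed) as supplementary analyses". SAP 16.1.8 says the same for the key secondary endpoints. In SAP Table 3 the mFAS is the only supplementary analysis listed for the primary and all five key secondary endpoints.

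The only scheduled APD334-308 endoscopy is at Week 52/Early Termination (Protocol 9.7.1.1 and Table 7). Footnote b to Table 7 exempts early leavers: "If a subject discontinues at or before Week 16, a sigmoidoscopy and biopsy are not required". Protocol 5.1 also waives the Early Termination endoscopy if one was done in the preceding 4 weeks.

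**The concern.** Two rules in the SAP treat the same subject differently. Under 16.1.2 a subject who starts rescue medication soon after Week 12 and leaves the study has a known outcome. Under 5.5 that subject may have no qualifying measurement and so falls outside the analysis set for some endpoints. The exclusion is then linked to outcome: it removes failures and cannot remove responders.

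This differs from the usual question of how to treat missing data, because the SAP itself says these outcomes are not missing. Protocol 10.4 takes the same position for its treatment failures.

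The supplementary role of the mFAS limits the harm, but it is the only such analysis left. SAP 5.4 drops the Per Protocol efficacy analyses, and the multiple-imputation, tipping-point and copy-reference analyses in Protocol 10.4 are not carried into the SAP. A reader comparing the FAS and mFAS results would see a change that mixes two things: removal of subjects whose outcome is truly unknown, and removal of subjects whose outcome is known to be failure.

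**Working it through.** **Step 1. Can a known failure lack an APD334-308 endoscopy?** Yes. One endoscopy is scheduled, and it is waived for discontinuation at or before Week 16. The 4-week waiver, counted from the APD334-302 Week 12 endoscopy, also runs to about Week 16, so the two waivers largely cover the same people. A procedure that prevents endoscopy, or a missed Early Termination endoscopy, adds a few more. A known failure who has an Early Termination endoscopy meets the entry rule.

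**Step 2. Which endpoints are affected?** The components come from the definitions in SAP 16.

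| Endpoint | Components | Known failure with no APD334-308 endoscopy |
|---|---|---|
| Endoscopic improvement | ES | Outside the mFAS |
| Mucosal healing | ES, Geboes | Outside the mFAS |
| Clinical remission | SF, RB, ES | Outside if an ES is needed; inside if SF or RB is enough |
| Corticosteroid-free clinical remission | As above, plus steroid history | As above |
| Sustained clinical remission | As above, at Weeks 12 and 52 | As above |
| Symptomatic remission | SF, RB | Inside if any post-enrolment SF/RB data exist |

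SF and RB come from the daily eDiary, so the last row is largely unaffected.

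**Step 3. Does as-observed keep the failures who do enter?** The SAP does not say. For endoscopy-based endpoints, SAP Table 2 maps Days 66 to 113 to Week 12 and Days 337 to 393 to Week 52 (both windows are longer for COVID-19-affected visits). An Early Termination endoscopy on, say, Day 210 maps to neither. Such a subject is in the mFAS but has no observed Week 52 value. Whether the subject counts as a nonresponder depends on whether 16.1.2 still governs the as-observed analysis.

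**Step 4. Size.** The plan states no figure to reproduce: SAP 7 has no formal sample size, and the documents give no remission rates and no count of affected subjects. The inputs below are therefore assumptions, apart from the planned 35 subjects and the 2:1 parent-study ratio. These give 35 × 2/3 = 23.3 and 35/3 = 11.7, taken as 23 etrasimod and 12 placebo. The SAP notes that the central randomization did not control balance within Japan.

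If an arm has r responders among n subjects and k known nonresponders are removed, its rate rises by

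r/(n − k) − r/n = rk / [n(n − k)].

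With k = 3:

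- Placebo 1/12: 1 × 3/(12 × 9) = 2.8 points
- Placebo 2/12: 2 × 3/(12 × 9) = 5.6 points
- Etrasimod 7/23: 7 × 3/(23 × 20) = 4.6 points

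Effect on the difference, with p-values from Fisher's exact test:

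| Assumed responders | All kept | 3 lost from placebo | 3 lost from etrasimod | 2 lost from each arm |
|---|---|---|---|---|
| 7/23 vs 1/12 | 30.4% − 8.3% = 22.1 (p = 0.216) | 30.4% − 11.1% = 19.3 (p = 0.386) | 35.0% − 8.3% = 26.7 (p = 0.204) | 33.3% − 10.0% = 23.3 (p = 0.222) |
| 7/23 vs 2/12 | 30.4% − 16.7% = 13.8 (p = 0.450) | 30.4% − 22.2% = 8.2 (p = 1.000) | 35.0% − 16.7% = 18.3 (p = 0.422) | 33.3% − 20.0% = 13.3 (p = 0.677) |

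When 0 to 4 subjects are lost from one arm only, the difference ranges from 17.9 to 28.5 points in the first row and from 5.4 to 20.2 in the second. Roughly equal losses nearly cancel.

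**The case against.** The strongest reply is that SAP 5.5 never names endoscopy. It speaks of measurement of the MMS or any component score, so an SF or RB score might admit a subject for clinical remission, and 16.1.2 would then make that subject a nonresponder. This stands for the three clinical-remission composites. A reader might infer that five of the six primary and key secondary endpoints definitely lose known failures, or that all supplementary remission analyses do. The text does not support either, because the qualifying measurement for a composite is undefined and symptomatic remission needs no endoscopy. The reply does not reach endoscopic improvement or mucosal healing, which have no SF or RB component.

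A second reply is that 16.1.2 assigns nonresponse for all efficacy endpoints, so counting that outcome as observed is a natural reading. It may be what was intended, but neither 5.5 nor 16.1.4/16.1.8 lets an assigned outcome satisfy the entry rule.

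Third, the group is small. It is mainly subjects who stop within about four weeks of choosing to continue. After that an Early Termination endoscopy is scheduled, and early entry to the open-label extension requires one. This stands.

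Fourth, the estimates are too imprecise for a few points to matter. With 8/23 vs 2/12 (assumed), the Wald 95% half-width is 1.96 × √(0.348 × 0.652/23 + 0.167 × 0.833/12), about 29 points. This also stands as a limit on importance. It does not justify leaving the rule ambiguous.

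Finally, Protocol 10.3 already planned a similar set, and contrasting observed data with nonresponder imputation is a recognised approach. That contrast is meant to test the handling of unknown outcomes, and these outcomes are known.

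**Conclusion.** The inconsistency is real and limited. On the endpoint-specific rule as written, known failures without an APD334-308 endoscopy leave the mFAS for endoscopic improvement and mucosal healing. For clinical, corticosteroid-free and sustained remission they leave only if an endoscopic score is required, which the SAP does not settle.

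Each exclusion raises the supplementary rate in its own arm, or leaves it unchanged if that arm has no responders. A reader might infer a bias in a fixed direction. The documents do not support that: losses in placebo shrink the difference, losses in etrasimod enlarge it, and nothing says which arm would lose more. The shift of about 3 to 6 points rests on an assumed 23/12 split, assumed responder counts, and three affected subjects all in one arm. It is an illustration and not a forecast.

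Nor does the point extend to the primary analyses. These use the FAS with every missing outcome counted as nonresponse, so all of these subjects are retained there.

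**What to change.** - SAP 5.5: state that, for binary responder endpoints, a dosed subject with a Baseline also qualifies for the mFAS, as a nonresponder, if a known nonresponse under 16.1.2 (scenarios 1 to 4) occurred before the assessment.
- SAP 16.1.4 and 16.1.8: state that as-observed data include these known nonresponses, whether or not a value falls in the Week 52 window.
- SAP 5.5: define which component or components count as a measurement for composite endpoints.

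If exclusion was intended, the SAP should say so and report the number of excluded known failures by arm and endpoint.

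The cost is a few sentences and a small change to the mFAS flag derivation, with no new data. The downside is slightly lower reported response rates in the supplementary tables.
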